² Treatment Year 1 and 2 will continue with the same frequency of visits and collections until week 104 or until the patient is transplanted. Visit intervals and examinations/samplings will be kept the same throughout year 1 and 2 of the continued treatment period.

³ For patients who did not have a Speckle Tracking/Traditional Echocardiography performed at screening, an effort will be made to perform this examination before start of continued treatment.

⁴ Speckle Tracking/Traditional Echocardiography will be repeated every 6th month during year 1 and 2 of the continued treatment period in weeks 0, 24, 48, 72 and 104.

Illustration of the study design - continued treatment Year 3

Continued Treatment Period Year 3				
Week	116	128	140	156
Clinic visit	X		X	X
Plasma oxalate	X	X	X	X
STE ¹		X		X
Stool	X	X	X	X
Safety labs	X	X	X	X

¹ Speckle Tracking/Traditional Echocardiography will be repeated every 6th month during the continued treatment period year 3, in weeks 128 and 156.

Number of patients (planned):

Approximately 6 to 12 patients will be enrolled in the study, it is estimated that 2 of these patients will be children.

Diagnosis and main criteria for inclusion:

Main Inclusion Criteria:

1. Signed informed consent (as applicable for the age of the patient). An appendix to the informed consent form will be signed by patients continuing on treatment after week 14.
2. Male or female patients \geq 2 years of age. Patients have to be able to swallow size 4 capsules twice daily, or use a gastric tube that allows for administration of size 4 capsules.
3. A diagnosis of PH (as determined by standard diagnostic methods).
4. Patient should be on a stable dialysis regimen for at least two weeks before baseline.
5. Plasma oxalate \geq 40 micromole/L prior to the dialysis session.
6. Patients receiving vitamin B6 must be receiving a stable dose for at least 3 months prior to screening and must remain on the stable dose during the study. Patients not receiving vitamin B6 at study entry must be willing to refrain from initiating vitamin B6 during study participation.

Main Exclusion Criteria:

7. Inability to swallow size 4 capsules twice daily, or using a gastric tube not suited for administration of size 4 capsules via the tube.
8. Ongoing treatment with immunosuppressive medication.

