6.2.1 Screening

Patient Information must be given and the Informed Consent form must be signed prior to any study related procedures being performed. The investigator shall list all patients who are considered for participation in the study and who have signed the Informed Consent on a Screening and Inclusion log.

The inclusion and exclusion criteria should be reviewed. Demographics and baseline data will be collected. These include:

- Birthdate, height, weight.
- Physical examination and Vital Signs.
- PH medical history (including diagnosis, historical levels of urinary oxalate, renal function).
- Other medical history, including concurrent illnesses and symptoms.
- Concomitant medication.

The following samples should be taken and sent for analysis:

- Haematology analyses, clinical chemistry analyses and pregnancy test.
- Urine sample for urinalysis, if possible.

The patient should be on a stable dialysis regimen individualised to remove adequate oxalate to minimise the risk for systemic oxalosis for at least two weeks prior to baseline (two weeks before visit week 2). The regimen could be either HD or PD or a combination of HD and PD. The PD regimen (number of days/week, hours per treatment, volume of dialysis buffer) and HD regimen (number of days/week; hours per treatment; blood and dialysate flow rates; and HD membrane) will be maintained unchanged for the duration of the study. This will be monitored and recorded by measuring volume of spent dialysate from HD and PD and quantifying dialysis dose of each HD session in terms of Kt/V measurement using an online clearance monitor.

Speckle Tracking Echocardiography and traditional echocardiography will be performed, if possible, at screening visit (+/- 1 month) or before start of continued treatment period (at visit week 14). Speckle Tracking Echocardiography will then be repeated at week 24 in the continued treatment period and thereafter every 6 months until end of treatment, if possible.

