7 SELECTION AND WITHDRAWAL OF PATIENTS

7.1 Patient inclusion criteria

1. Signed informed consent (as applicable for the age of the patient). An appendix to the informed consent form will be signed by patients continuing on treatment after week 14.
2. Male or female patients \geq 2 years of age. Patients have to be able to swallow size 4 capsules twice daily, or use a gastric tube that allows for administration of size 4 capsules.
3. A diagnosis of PH (as determined by standard diagnostic methods).
4. Patient should be on a stable dialysis regimen for at least two weeks before baseline.
5. Plasma oxalate \geq 40 micromole/L prior to the dialysis session.
6. Patients receiving vitamin B6 must be receiving a stable dose for at least 3 months prior to screening and must remain on the stable dose during the study. Patients not receiving vitamin B6 at study entry must be willing to refrain from initiating vitamin B6 during study participation.

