11.5.1.2 Safety data for the ongoing studies OC5-OL-01, OC5-DB-02 and OC5-OL-02

The current OC5-OL-01 study started in May 2014 and is ongoing in Germany. Fourteen subjects were screened and 12 subjects have been enrolled in the study and received study drug. This study includes late-stage patients with ESRD who are on dialysis. Most of these patients are on a waiting list for transplantation. Eight subjects continued into the continued treatment phase of the study, and one subject currently remains in the study (as of September 2019). There have been no severe nor serious related AEs for Oxabact® in this ongoing study.

In the ongoing, double-blind OC5-DB-02 study in patients with retained but reduced kidney function (eGFR <90ml/hr/1.73m²), 16 patients have been randomised. There have been 8 SAEs reported to-date; none of them was considered related to study drug. There have been no reported SAEs in the ongoing open-label OC5-OL-02 study (currently 4 enrolled patients).

Overall, the safety data accrued to date would suggest that the OC5 drug product is safe and well tolerated and appears to have a similar safety profile as the earlier OC3 drug product. Further safety information of the OC5-OL-01, OC5-DB-02 and OC5-OL-02 studies has been detailed in the current version of the Oxabact® Investigator's Brochure.

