2.4 Sample size

Approximately 6 to 12 patients will be enrolled in the study, to have a minimum of 6 patients completing the first year of continued treatment (i.e. week 52). It is estimated that 2 of the enrolled patients will be children.

The sample size is not based on assumptions of efficacy outcome and statistical power. Any inferences from the data will be based on clinical relevance rather than statistical significance.

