If possible, a correlation analysis between *O.formigenes* and total plasma oxalate will be done as well. A repeated measures model can be used to determine the "repeated measures correlation" between total number of *O.formigenes*, or one of the genotypes with sufficient data, and total plasma oxalate. Note that the limiting factor here is the count data for *O.formigenes*: this type of data generally deviates from normality. Therefore, for this correlation analysis, the total number of *O.formigenes* may be log transformed by executing $\ln(O.formigenes)$ where \ln is the natural logarithm. If this transformation does not suffice, another transformation may be used, however it should be noted that it is possible that no transformation will suffice with the desired effect of reaching normality, therefore results should be considered with caution. The correlation coefficient will be presented in a table.

Speckle Tracking/Traditional Echocardiography

Change in Speckle Tracking/Traditional Echocardiography parameters, collected at screening and during continued treatment, will be calculated at each visit as the visit minus the baseline value.

Speckle Tracking Echocardiography (STE) parameters are Image Quality, Global Longitudinal Strain (GLS), Global Circumferential Strain (GCS), Rotational Displacement, Average Apical Longitudinal Strain, Average Mid Longitudinal Strain, Average Basal Longitudinal Strain and Relative Apical Longitudinal Strain (RALS; defined as Average Apical Longitudinal Strain / (Average Basal Longitudinal Strain + Average Mid Longitudinal Strain)).

Traditional Echocardiography (TE) parameters are Left Ventricular Ejection Fraction (LVEF), Left Ventricular Mass Index (LVMI), Left Ventricular End Diastolic (LVED) Dimension, Interventricular Septal (IS) Thickness at End-diastole, Pulse Wave doppler (PW) Thickness at End-diastole, e/é, e/a, Tricuspid Regurgitation and Continuous Wave Doppler.

Summary statistics of the parameters will be presented on a per-visit basis. For all parameters (except for Image Quality and Tricuspid Regurgitation), both the actual value as well as the change from baseline value will be presented. For Image Quality and Tricuspid Regurgitation, the number/percentage of observations in the different categories will be presented per visit. STE parameters and TE parameters will be presented in separate tables for the FAS and mFAS.

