6.7.3 Vital Signs

Vital sign data consist of measurements for body weight, pulse rate, systolic and diastolic blood pressure, temperature and respiration rate. Vital signs will be summarized (limited to: n, mean, SD, median, minimum and maximum) and listed per visit, using protocol visits. Change from baseline will be calculated and presented as well, using the same summary statistics. If applicable, vital sign measurements collected as additional/unscheduled assessments (i.e. apart from those per protocol) will only be listed and will not be used in summary statistics.

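### Raw changes in LV dimension and wall thickness pool children with adults for up to about 39 months, so a child's growth can appear as cardiac change in three rows of SAP table 14.2.30

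*SAP*

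**What the plan says.** SAP 6.6.2 (Speckle Tracking/Traditional Echocardiography) names the traditional parameters. Three are absolute size measures: "Left Ventricular End Diastolic (LVED) Dimension, Interventricular Septal (IS) Thickness at End-diastole" and a 'PW' thickness at end-diastole, which I read as a wall thickness because it is called a thickness. LV mass is the only size measure given as an index.

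Change is the visit value minus baseline. SAP 6.1 takes baseline from screening, or from continued-treatment week 0 if screening is missing. Actual values and changes are summarised by visit, in tables for the whole FAS and the whole mFAS. Neither document mentions body-size indexing of these three measures, z-scores, age adjustment or an adult/child split for echocardiography.

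Protocol 7.1 admits patients from 2 years of age. SAP 2.4 states: "It is estimated that 2 of the enrolled patients will be children". Protocol 11.5.1.2 reports that "12 subjects have been enrolled in the study and received study drug", that eight went on to continued treatment, and that one remained in September 2019. Echocardiography is scheduled up to continued-treatment week 156 (Protocol 6.1, Figure 8).

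Protocol 10.3 includes LV end-diastolic dimension, but not wall thickness, among the parameters by which a positive treatment effect would be judged.

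**The concern.** Chamber size and wall thickness increase as a child grows. An unindexed difference over roughly three years therefore contains growth as well as any cardiac effect, and a mean over adults and children together cannot separate the two. A larger ventricle reads as dilation and a thicker wall as hypertrophy. If the heart is in fact improving, growth can cancel the improvement.

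Echocardiographic change is a named secondary endpoint. SAP 2.4 says "The sample size is not based on assumptions of efficacy outcome and statistical power" and bases inference on clinical relevance, so the descriptive tables themselves are the evidence. With at most eight continuers, one or two children can move a mean noticeably. Because SAP 6.2 imputes nothing here, the share of children in each visit mean also changes as patients leave. The actual-value rows are affected too: their mean moves when a small patient enters or leaves the denominator.

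**Working it through.** The documents give no effect size, variability or power figure for echocardiography, so there is no planned number to reproduce. The check is of how far growth alone can move the pooled mean.

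**Inputs from the documents**
- Longest follow-up: 14 + 156 = 170 weeks; 170 × 7 / 30.4375 = 39.1 months.
- Patients contributing: follow-up echocardiography takes place in continued treatment, so at most 8 patients have a change value at those visits, in the FAS rows as well as the mFAS rows.
- Children: 2 estimated among those enrolled. The number and ages of children treated or continuing are not given, so 0, 1 and 2 are all shown.

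**Assumptions, not in the documents**
- Growth per child over the full follow-up: 2, 5 or 8 mm in LVED dimension; 0.5, 1.0 or 1.5 mm in wall thickness.
- True cardiac change is zero in every patient.

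**Formula:** shift in mean change = (children at visit ÷ patients at visit) × growth per child.

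| Children among 8 patients | LVED shift for 2 / 5 / 8 mm growth | Wall shift for 0.5 / 1.0 / 1.5 mm growth |
|---|---|---|
| 0 | 0 | 0 |
| 1 | 0.25 / 0.62 / 1.00 mm | 0.06 / 0.12 / 0.19 mm |
| 2 | 0.50 / 1.25 / 2.00 mm | 0.12 / 0.25 / 0.38 mm |

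Example: 2/8 × 5 mm = 1.25 mm.

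**Drop-out.** Keep two children at 5 mm each and let adults leave:
- 6 adults left: 2/8 × 5 = 1.25 mm
- 4 adults left: 2/6 × 5 = 1.67 mm
- 2 adults left: 2/4 × 5 = 2.50 mm
- no adults left: 5.00 mm

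The displayed mean would rise from 1.25 to 2.50 mm through a change of composition alone, with no heart changing. These compositions are illustrations; the documents do not say who leaves.

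**Median.** With six adults at 0 and two children at 5 mm, the median change is 0 while the mean is 1.25 mm. With two adults and two children it is (0 + 5)/2 = 2.5 mm. The median helps early and less after drop-out.

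**The case against.** The case for leaving the plan alone is substantial. SAP 6.1 calls all evaluations exploratory and plans no formal significance testing, and Protocol 12.1 frames efficacy as a combined evaluation of individual case studies. The plots and the comparisons with plasma oxalate use GLS, LVEF and RALS, none of them a raw dimension. Listing 16.2.6.4 gives each patient's traditional echo values and listing 16.2.4.1 the demographics, so a reader can pick out the children. The summaries also show median, quartiles and range. The interim question in SAP 6.3 concerns cardiac function, whereas these three measures describe structure. Echocardiography is done only if possible, so a child may have no usable pair of values. Growth also runs towards apparent worsening, so it would not create false evidence of benefit in these rows.

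All of this stands and limits the severity. It does not correct the pooled rows. Protocol 10.3 counts LVED dimension towards a positive effect, masked improvement remains possible, and the listing gives raw values that the reader would have to relate to body size unaided. A case-study approach also sits badly with averaging a growing child and adults.

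Three stronger readings may tempt a reader.
- **LVMI uses an outdated height.** The screening section of the protocol lists "Birthdate, height, weight", and SAP 6.7.3 says "Vital sign data consist of measurements for body weight, pulse rate, systolic and diastolic blood pressure, temperature and respiration rate", with no height. But neither document says how LVMI is derived or which height enters it, so this does not follow.
- **A percentage bias can be quoted for the trial.** The planned output is absolute change, and nothing places both children among the continuers.
- **The plan will declare growth to be a cardiac effect.** It only tabulates these values; the misreading is possible, not prescribed.

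**Conclusion.** The point holds for three rows of table 14.2.30: LVED dimension, septal thickness and 'PW' thickness. As written, the pooled raw change mixes growth with cardiac change whenever a child contributes. It does not extend to LVEF and RALS, which are ratios, or to LVMI, which is already indexed.

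The size is conditional. For LVED dimension at n = 8, with 2 to 8 mm assumed growth per child, the shift is 0 with no children, 0.25 to 1.0 mm with one and 0.5 to 2.0 mm with two, and larger if adults leave first. The growth figures are assumptions; children on dialysis may grow less, and the actual number and ages of children are not given. Since the endpoint is secondary and descriptive and individual values are listed, this is a worthwhile improvement in presentation and not a threat to the primary analysis.

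**What to change.** In SAP 6.6.2 and table 14.2.30, restrict the pooled actual-value and change-from-baseline summaries of LVED dimension, septal thickness and 'PW' thickness to adults. Present patients under 18 individually beside them. Where clinic records hold a height close to the echo date, add body-size-indexed values or z-scores for these patients, and name in the SAP the index or reference used. Where no such height exists, show the raw values with age and say that growth cannot be separated.

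The core change needs only data already collected: SAP wording, an age flag and a revised table shell before the final tables are run. The optional indexing needs a search of clinic records. New prospective height measurements are not worth adding: one patient remained in September 2019, so they could inform almost nobody, and they would need a protocol amendment.

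The downside is fewer patients in the three pooled rows, which may become very sparse at late visits.

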2.5 Study flow chart

Table 1 Schedule of assessments – the first 14 weeks of the study

Study period:	Screening	Baseline				Treatment						Post-treatment			
Week:	-4 – 0 "0"	1	2	3	4	5	6	7	8	9	10	11	12	13	14
Clinic visit	1		2		3		4		5		6		7		8
Incl/Excl criteria¹	X				X										
Demographics	X														
Vital signs	X														X
Physical exam	X				X						X				X
PH Med History	X														
Medical history	X														
Concomitant med	X	X	X	X	X	X	X	X	X	X	X	X	X	X	
Pregnancy test	X														
Plasma oxalate		X	X	X	X	X	X	X	X	X	X	X	X	X	
Faeces			X							X					X
Safety Labs²	X			X						X					X
Treatment					X	X	X	X	X	X					
Adverse events						X		X		X		X		X	
Speckle Tracking Echocardiography	X ³														

1. Eligibility criteria will be evaluated at Screening and after Baseline. A stable dialysis regimen should be maintained for 2 weeks before start of baseline (2 weeks before visit week 2) and during the whole study.

2. Safety labs include: haematology analysis, clinical chemistry analysis and urinalysis and will be analysed at the local lab. Safety labs will be analysed at screening visit and at week 4, 10 and 14 +/- 1 week.

3. Speckle Tracking Echocardiography and traditional echocardiography should be done at screening visit +/- 1 month.

Table 2 Schedule of assessments – continued treatment Year 1 and 2

Study period	Continued treatment Year 1 and 2								
Week	0	4	8	12	16	20	24	28	32 ¹
Clinic visit	9 ²	10 ³	11	12	13	14	15	16	17
Vital signs			X		X		X		X
Physical exam			X		X		X		X
Concomitant med	X	X	X	X	X	X	X	X	X
Plasma oxalate	X	X	X	X	X	X	X	X	X
Faeces			X		X		X		X
Safety Labs⁴	X	X	X	X	X	X	X	X	X
Pregnancy test⁵	X						X		
Treatment	X	X	X	X	X	X	X	X	X
Adverse events	X	X	X	X	X	X	X	X	X
Speckle Tracking Echocardiography	(X) ⁶						X ⁷		

¹. Treatment will continue until the patient is transplanted. The maximal length of the continued treatment period will be 36 months. Visit intervals and examinations/samplings will be kept the same throughout the year 1 and 2 of the continued treatment period.

² Visit 9 may coincide with visit 8 for patients continuing on treatment immediately after week 14 visit.

³. Visit 10 will be scheduled 28 days (+/- 3 days) after first day of continued treatment after study week 14.

⁴. Safety labs include: haematology analysis, clinical chemistry analysis and urinalysis and will be analysed at the local lab.

⁵. Pregnancy test will be repeated every 6 months during the continued treatment period.

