6 STATISTICAL ANALYSIS

6.1 General considerations

All evaluations will be explorative in nature, unless stated otherwise. There will be no formal statistical significance testing.

Raw data (in listings) will be presented in the same precision as received. Appropriate rounding will be performed for the summary statistics: arithmetic mean, median, SD (standard deviation) and two-sided 95% confidence limits will be presented with one more decimal than the original data; minimum and maximum values will be presented with the same precision as the original data. In special cases, e.g. after conversion of data, the number of decimals will be determined based on relevance. In frequency tables, percentages will be presented with 1 decimal unless otherwise stated. P-values will be presented with 3 decimals, and those smaller than 0.001 will be replaced by <0.001.

Descriptive statistics presented in summary tables for continuous variables will be the number of non-missing observations (n), arithmetic mean, SD, SE, median, Q1 and Q3, minimum and maximum. All plots will be created using scheduled protocol time or visit on the x-axis. Mean plots will be presenting mean +/- SE. For qualitative data, frequency counts and percentages will be determined. The denominator used when calculating percentages will be the number of subjects in the applicable analysis population.

Baseline is generally defined as the last non-missing and valid measurement/assessment before first dose of study drug. Unscheduled measurements are excluded as baseline value, unless otherwise specified. Change from baseline is calculated as the value at a specific time point minus the value at baseline. For this study, the following definitions are used to define the baseline measurement:

Vital signs: The screening value is used as baseline.

Plasma oxalate: The primary baseline is defined as an average of the available baseline measurements at weeks 2 and 4 (i.e. Visits 2 and 3 respectively). If one baseline measurement is missing for plasma oxalate, the remaining value will be used as baseline value. An additional baseline is the week 10 (Visit 6) assessment of plasma oxalate levels which will serve (only) as a baseline for the assessment of the change in plasma oxalate levels following the 4 week off-treatment period (secondary endpoint). For analyses in the CT phase of the study, a third baseline is defined, being the week 14 value at week 14 of the initial TRT phase.

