Faeces: The measurement at week 4 is considered the baseline value.

Echography: The screening value is used as baseline. If this value is missing, the CT week 0 value is used as baseline value instead.

Safety lab: Safety lab is determined at screening and at week 4. The week 4 measurement is considered the baseline value. If this value is missing, the screening value will be used instead.

Data for screening failures will not be presented in summary tables, except for disposition and end-of-study displays, provided end-of-study data includes screen failures. Data for screening failures will be listed as available.

For this study, a treatment emergent adverse event (TEAE) is defined as an adverse event reported on or after first dose of study treatment. AEs after last dose date, and thus also after study drop-out, are not collected.

All descriptive statistics tables will be presenting data per visit, if applicable.

Any statistical significance determined in the analyses will be viewed with caution, considering the very small and heterogeneous patient population. Any determined p-values can only be indicative. No correction for multiple comparisons will be applied for any of the endpoints.

All collected data will be presented as is in individual data listings, and no other (calculated) data will be added unless specifically specified in the respective section. In case derived variables are to be added to the listings, both the original variable as well as the derived will be presented. For all relevant listings, study day will be added. The calculation for this day is as described in section 9.1.

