To visualize the effects through time graphically, the following plots will be created for FAS and mFAS, using the overall treatment period:

- Mean +/- SE and individual plots will be created for GLS/LVEF/RALS values through time. Presentations are made for the actual values and the CFB values.
- Combined spaghetti plots will be created using the actual values. No spaghetti plots will be created for change from baseline.
- Furthermore, the relationship between GLS/LVEF/RALS and total plasma oxalate/free plasma oxalate over time will be evaluated graphically. These comprise of:
 - Mean +/- SE and individual plots plotting the time course of GLS/LVEF/RALS and total plasma oxalate/free plasma oxalate in one graph using double axes.

- Individual scatterplots and a combined scatterplot of GLS/LVEF/RALS versus total plasma oxalate/free plasma oxalate. For these plots, only time points can be used when both assessments were made, where 'baseline' is considered the same time point even if assessed at different weeks.

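### Where the screening echo is missing, the echo–oxalate scatterplots can join a week-14-or-later echo to pre-drug oxalate, and the SAP leaves the oxalate baseline for these plots unsettled

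*SAP*

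**What the plan says.** SAP 6.1 first gives a general rule: "Baseline is generally defined as the last non-missing and valid measurement/assessment before first dose of study drug". It then sets study-specific baselines.

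- **Echo:** "Echography: The screening value is used as baseline". The fallback follows: "If this value is missing, the CT week 0 value is used as baseline value instead".
- **Plasma oxalate, primary:** "The primary baseline is defined as an average of the available baseline measurements at weeks 2 and 4".
- **Plasma oxalate, CT phase:** "For analyses in the CT phase of the study, a third baseline is defined, being the week 14 value".

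For the scatterplots, SAP 6.6.2 uses the same wording for faeces and for echo: "For these plots, only time points can be used when both assessments were made", with the exception "where 'baseline' is considered the same time point even if assessed at different weeks". The echo part of 6.6.2 says that the plots cover the overall treatment period. The output list in SAP 10.3 labels the same displays (14.2.31–14.2.43) as CT.

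SAP Table 2 schedules plasma oxalate at CT week 0, which is visit 9. Its footnote lets visit 9 coincide with visit 8 "for patients continuing on treatment immediately after week 14 visit".

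**The concern.** For faeces the pooling rule is harmless. The faecal baseline is week 4 and the oxalate baseline is weeks 2 and 4, so both precede the first dose.

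For echo it is harmless only when the screening examination exists. A CT week 0 echo comes after a full course of OC5 and a washout. If the shared label joins it to the week 2/4 oxalate average, the plotted point combines two different disease and treatment states. This can create or hide an apparent relation between cardiac function and oxalate.

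The same substitution enters the echo change-from-baseline tables (14.2.29–14.2.30) and plots. For a fallback patient, any cardiac change in the first 14 weeks drops out of the change, and nothing tells the reader so.

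Individual points carry weight here. Protocol 12.1 takes the evidence for efficacy from individual case studies considered together, and cardiac function is one of the two interim aims in SAP 6.3.

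**Working it through.** The plan states no figure for this point, so the check sets the baseline rules against the visit schedule.

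**Inputs**
- OC5 in study weeks 5–10 (Protocol 6.2.3): 10 − 5 + 1 = 6 weeks on drug.
- Off drug in weeks 11–14 (Protocol 6.2.4): 14 − 10 = 4 weeks.
- CT week 0 is study week 14 at the earliest (SAP Table 2 footnote), so the washout is at least 4 weeks.
- Primary oxalate baseline: average of weeks 2 and 4 (SAP 6.1).
- CT-phase oxalate baseline: week 14 (SAP 6.1).
- Later echoes: CT weeks 24, 48, 72, 104, 128 and 156 (SAP Tables 2 and 3).
- Patients who entered continued treatment: 8 of the 12 treated (Protocol 11.5.1.2).

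**Gap for a fallback patient under SAP 6.6.2**
- From week 2: 14 − 2 = 12 weeks. From week 4: 14 − 4 = 10 weeks. From the mean of the two weeks: 14 − 3 = 11 weeks.
- These are minima, because visit 9 may fall after week 14.

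**The two readings side by side**

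| Echo used as baseline | 6.6.2: overall period, oxalate weeks 2/4 | 10.3: CT, oxalate week 14 |
|---|---|---|
| Screening | Both values pre-drug | Pre-drug echo with post-course oxalate, nominally 14 − 0 = 14 weeks apart (echo window ±1 month) |
| CT week 0 | Post-course echo with pre-drug oxalate, at least 10–12 weeks apart | Same visit if visits 8 and 9 coincide, otherwise the week 14 visit before it |

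Each reading aligns one group and misaligns the other. SAP 6.1 gives echo no separate CT-phase baseline that would bring the screening-echo group into line.

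**Share of one fallback patient's points**

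Share = 1 / (1 + number of later scheduled echoes).
- Followed to CT week 24: 1/(1 + 1) = 1 of 2.
- To week 52: 1/(1 + 2) = 1 of 3.
- To week 104: 1/(1 + 4) = 1 of 5.
- To week 156: 1/(1 + 6) = 1 of 7.

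A patient with a screening echo may also have a CT week 0 echo, giving up to 8 points.

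**Size of the displacement**

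The error on the oxalate axis equals the change in oxalate between the week 2/4 average and CT week 0. The documents give no value for it. By assumption only, take a baseline of 40 µmol/L (the entry threshold) to 120 µmol/L and a change of −30% to +10%:
- At 40: 40 × (−0.30) = −12 to 40 × 0.10 = +4 µmol/L.
- At 120: 120 × (−0.30) = −36 to 120 × 0.10 = +12 µmol/L.

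With the CT week 0 oxalate used instead, the gap for a fallback patient is zero and so is the displacement.

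**The case against.** The strongest objection is that the SAP may already align the fallback patients. Section 10.3 labels the plots CT, and 6.1 sets week 14 as the oxalate baseline for CT-phase analyses, which is close to the remedy. This reading is real, so it cannot be stated as fact that the oxalate is pre-drug. It does not settle the matter, because it moves the mismatch to the patients with a screening echo and conflicts with 6.6.2.

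Other limits also stand.

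- The fallback is a disclosed, prespecified exception to the general baseline definition and follows the protocol's own echo schedule.
- The pooling rule governs the scatterplots only. SAP 6.6.2 also plans double-axis time courses of echo and oxalate with no such rule, so the scatterplots are not the only look at the relation.
- For echo and oxalate no coefficient, test or decision is planned; the repeated-measures correlation is for faeces.
- Individual plots and echo listings (16.2.6.3–16.2.6.4) let a careful reader see what happened.

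A reader might infer from the amendment dates that early patients lack a screening echo: the study started in May 2014, and the amendment describing speckle tracking at screening or week 14 is dated October 2014. The documents do not show this. That entry concerns speckle tracking, whereas ejection fraction is a traditional measure, and Protocol 10.3 provides for re-evaluating earlier examinations.

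A scheduled value is also not always a collected one. Before Amendment VII, free oxalate consists of whatever local results were available (Protocol 10.1), so a same-visit free value may be missing.

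**Conclusion.** The point holds for a limited group. Under SAP 6.6.2, a patient without a screening echo contributes one baseline point whose two values are at least 10–12 weeks apart, with 6 weeks of OC5 and at least 4 weeks off drug between first dose and echo. Under SAP 10.3, the patients with a screening echo are mis-paired instead. No single oxalate baseline suits both groups.

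One point per affected patient is involved. Fallback patients number at most 8 and possibly none.

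Three stronger conclusions are not supported. The echo–oxalate plots are not mis-paired for every patient under either reading. The fallback echo is not an on-treatment value, since it follows the washout. The change-from-baseline tables are not invalid; they mix two kinds of baseline without saying so. Because the displays are descriptive, this is a correction to make before the final outputs and does not undermine the primary analysis. The conclusion rests on the visit schedule being followed as written.

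**What to change.** 1. In SAP 6.6.2, choose the oxalate value by the echo actually used. A screening echo takes the week 2/4 average. A CT week 0 echo takes the CT week 0 oxalate (the week 14 value if visits 8 and 9 coincide), plotted at that week.
2. For a CT week 0 echo with no same-visit oxalate, omit the point. This may arise for free oxalate before Amendment VII.
3. Reconcile the overall treatment period in 6.6.2 with the CT label in 10.3, and state which oxalate baseline each display uses.
4. Flag fallback-baseline patients in tables 14.2.29–14.2.30 and in the echo change-from-baseline plots. Separate tables are not needed: with at most 8 continuing patients they could leave very small cells, and SAP 6.6.1 itself drops the dialysis subgroup summaries when a group has fewer than 3 patients.

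The cost is revised SAP wording and minor programming, with no new sampling. The downside is that a few scatterplot points may be lost.
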